6.1 STATISTICAL ANALYSIS

Data will be entered into SPSS statistical software. Normally distributed continuous data will be analysed with paired Student's t test. Chi square test will be used for categorical or nominal data and Mann- Whitney U test will be used on non-normally distributed or ordinal data.

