4.0 MATERIALS AND METHODOLOGY

4.1 STUDY DESIGN

Single centre, randomised controlled trial.

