4.4 METHODS

This is a randomised control trial involving multiparas at term (≥ 37 weeks) who are planned for IOL for various indications. Participant information sheet with be given to all potential recruits and any inquiries by the participants will be answered by the recruiting care provider. Written consent will be obtained from all participants.

All participants will undergo standard assessment by the care provider before their IOL; including their personal characteristics, obstetric assessment and fetal wellbeing (using a nonstress cardiotocogram) assessment.

Insertion of Foley Catheter

Participants will be positioned in the dorsal position. Bishop score will be ascertained during the vaginal examination prior to Foley insertion. A Foley catheter size 16F is then introduced through

the external os using either by digital or speculum method (at discretion of introducer). Once the tip of the catheter has passed the internal os by 4 to 5cm, the balloon will be inflated with 80ml of water and retracted so the balloon rests on the internal cervical os. The other end of the Foley catheter will be taped without tension to the medial aspect of the women's thigh. (19)

Randomisation

Randomisation will be performed and intention to treat revealed only after successful Foley insertion. Randomisation is done by opening the lowest number, sealed and opaque envelope that is available, assigned in strict order. Randomisation sequence will be generated using a random number generator at Random.org in random blocks of 4 or 8 sequence, generated by an investigator who is not involved in recruitment. Blinding is not possible due to the nature of the intervention.

Participants will be randomised into two trial arms: Foley removal following its insertion

1. at 6 hours

or

2. 12 hours

Trial will be closely monitored by the supervisors. Any serious adverse effects (SAE) will be reported to UMMC-MREC committee for discussion and review of the clinical trial.

Labour Induction Care

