4.5 SAMPLE SIZE CALCULATION

To calculate our sample size for the primary outcome, we obtained data from literature review on:

Primary outcome 1: Induction to delivery interval

Bleicher et al reported mean induction to delivery interval in the multiparous subgroup for 6 hours vs 12 hours double balloon placement as 18.0 hours with SD 6.8 vs 22.6 hours SD 8.2, p= 0.04 respectively, a mean reduction of 4.6 hours in favour of 6-hour placement.(14)

Using https://www.openepi.com/SampleSize/SSMean.htm and applying alpha of 0.02 (Bonferroni correction for 2 primary outcomes), t test, 80% power, 1 to 1 ratio, 18.0 hours with SD 6.8 vs 22.6 hours SD 8.2, 54 women are required per arm (total 104). Factoring in the possibility of non-normal data distribution requiring Mann Whitney U test application, we increase sample size by 15% and assuming 10% dropout, we plan to recruit $54 \times 1.15/0.9 = 69$ in each arm (N = 138 women)

For maternal satisfaction, assuming a 1-point difference in the 11-point 0-10 visual numerical rating scale (VNRS) to be clinically relevant. Using https://www.openepi.com/SampleSize/SSMean.htm and applying alpha of 0.02 (Bonferroni correction for 2 primary outcomes), t test, 80% power, VNRS standard deviation of 2 for both arms, 81 women are required per arm (total 162). Factoring in the Mann Whitney U test application as satisfaction score is ordinal, we increase sample size by 15% and assuming 10% dropout, we plan to recruit $81 \times 1.15/0.9 = 103.5$ in each arm (total of 207 women). We rounded the required sample size of participants up to N = 210 in total to adequately cover for both primary outcomes.

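### Section 6.1 names a paired t test although the two randomised arms are independent, so the standard error, confidence interval and p value would rest on an arbitrary pairing of women

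*Protocol*

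**What the plan says.** Section 6.1 sets the whole analysis rule in a few lines. For continuous outcomes it states "Normally distributed continuous data will be analysed with paired" Student's t test. For the rest, apart from categorical data (chi-square), it states "Mann- Whitney U test will be used on non-normally distributed or ordinal data". The sentence on the t test carries no restriction to within-woman change or to particular outcomes.

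The design is described in Section 4.1 as "Single centre, randomised controlled trial". Section 4.4 adds "Participants will be randomised into two trial arms: Foley removal following its insertion" at 6 or at 12 hours, with allocation by sequential sealed envelopes in "random blocks of 4 or 8 sequence". No matching, crossover or pairing of women appears anywhere in the protocol.

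Section 4.5 sizes the interval outcome by "applying alpha of 0.02 (Bonferroni correction for 2 primary outcomes), t test, 80% power, 1 to 1 ratio", with a separate mean and SD for each arm, and concludes that "54 women are required per arm" before inflation.

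**The concern.** A paired t test works on differences within natural pairs. Here each woman belongs to one arm and contributes one insertion-to-delivery interval, so she has no partner in the other arm. Randomisation blocks do not supply one: a balanced block of 4 holds two women per arm, and a block of 8 holds four, with nothing linking one woman to another.

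To run the named test, the analyst would have to line up rows of the two arms in some order that the protocol does not define. With equal arms the estimated mean difference is the same for every ordering, but its standard error, confidence interval and p value are not. With unequal arms, which the assumed 10% dropout makes likely, some women in the larger arm would have to be left out, and then the estimate itself depends on who is dropped.

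At stake is the test for the first primary outcome, if the interval is judged normal, and for any continuous secondary outcome judged normal. Satisfaction is not touched, because Section 4.5 calls it ordinal and Section 6.1 sends ordinal data to the Mann-Whitney U test.

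**Working it through.** **1. Which design do the sample-size figures assume?**

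Inputs from Section 4.5: 18.0 h (SD 6.8) against 22.6 h (SD 8.2), difference 4.6 h; satisfaction difference 1 point, SD 2 in each arm; alpha 0.02; power 80%; ratio 1:1. Sidedness is not stated; two-sided is taken here because it reproduces both figures.

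Formula for two independent means, per arm: n = (SD1² + SD2²)(z₁₋α/₂ + z₁₋β)² / δ².

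- (2.326 + 0.842)² = 10.04.
- Interval: (46.24 + 67.24) × 10.04 / 21.16 = 53.8, so 54. The protocol states 54.
- Satisfaction: (4 + 4) × 10.04 / 1 = 80.3, so 81. The protocol states 81.
- For comparison, one-sided 0.02 gives 45 and 68, and two-sided 0.025 gives 51 and 77. Neither matches.

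A paired calculation would need the SD of within-pair differences, or a correlation. Section 4.5 gives neither. With a correlation of 0.3, for example, the paired formula would give 38 pairs for the interval and 57 for satisfaction. It meets the stated 54 and 81 only at correlation zero, where it is the same as the independent formula.

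**2. What the pairing changes.**

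For n women per arm and a pairing that happens to have sample correlation r between partners:

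- independent test: t = d / √[(s1² + s2²)/n], with 2n − 2 degrees of freedom;
- paired test: t = d / √[(s1² + s2² − 2·r·s1·s2)/n], with n − 1 degrees of freedom.

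The numerator d is fixed. Only r depends on the pairing. For random pairing r centres on zero with SD about 1/√(n − 1).

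**3. Illustration.**

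Assumptions: normal data, the planning SDs, and 95 per arm (210/2 = 105; 105 × 0.9 = 94.5, rounded up). The mean difference is set so that the independent test gives p = 0.025.

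- Independent standard error: √(113.48/95) = 1.093 h.
- t for p = 0.025 on 188 degrees of freedom: 2.259, so d = 2.259 × 1.093 = 2.47 h.
- Paired test on 94 degrees of freedom: r = 0 gives p = 0.026; r = +0.2 gives p = 0.013; r = −0.2 gives p = 0.042.
- The critical value for 0.02 on 94 degrees of freedom is 2.367. It is passed when r exceeds [1 − (2.259/2.367)²] × 113.48/(2 × 6.8 × 8.2) ≈ 0.090. The SD of r is 1/√94 = 0.103, so the share of pairings is P(Z > 0.090/0.103) ≈ 0.19.
- Simulation with 20,000 random pairings of one such data set agrees: paired p from about 0.005 to 0.057, with about 19% below 0.02.

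**4. Long-run behaviour under random pairing (simulated, 95 per arm, alpha 0.02).**

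- Type I error: about 0.019 for both the paired and the independent test.
- Power at 4.6 h: about 96.5% paired against 96.8% independent.
- At 54 per arm, power is 77.4% paired against 78.7% independent.

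**The case against.** Four points can be made for leaving this alone.

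- **It is probably a slip for unpaired.** The sample-size method and the Mann-Whitney alternative both belong to independent groups, so the intended comparison is fairly clear. That stands as an account of how the wording arose. It does not correct the text, which is the protocol's only statement of the test for normally distributed continuous data.
- **The paired test may be meant for change within a woman.** The only before-and-after measure is the Bishop score. It is an ordinal score, and the trial question would still need its change compared between arms. The sentence carries no such limit. This does not stand.
- **The interval may prove non-normal, so that the t test is never used on it.** Section 4.5 does foresee this. It limits the reach of the error but does not remove it: the same section plans with a t test first, and normally distributed secondary outcomes follow the same rule.
- **The practical damage is small.** On average this is right, as the long-run figures show.

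A reader might go further and infer that the paired test inflates the false-positive rate. The documents do not support that. A large inflation appears only if the file is sorted by outcome within each arm before pairing (about 67% at alpha 0.02 with the planning SDs, about 75% with equal SDs). Nothing in the protocol suggests such sorting. A reader might also infer that both primary outcomes are affected; satisfaction is not.

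**Conclusion.** The concern holds. Section 6.1 names a test that contradicts the design in Sections 4.1 and 4.4, the calculation in Section 4.5 and its own non-parametric alternative. The consequence is a result that is not uniquely defined: near the significance threshold, the same women and the same data can fall on either side of 0.02 according to the row order. In the example, a result that is not significant by the appropriate test (p = 0.025 against 0.02) becomes significant in about one random pairing in five.

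Away from the threshold the conclusion would rarely change. These sizes assume normal data, equal arms of 95, the planning SDs and pairing unrelated to outcome. That the wrong test is named does not depend on those assumptions.

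**What to change.** In Section 6.1, replace the paired Student's t test by an independent two-sample t test for comparisons between the arms. Welch's form is a reasonable option because the planning SDs differ (6.8 and 8.2), but the documents do not require it, and with equal arms it gave practically the same rejection rates as Student's form in simulation.

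If a within-woman comparison is wanted as well, it should be named separately as descriptive, since it is not the randomised comparison.

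The cost is a wording amendment. The 54 and 81 per arm already assume independent groups: 54 × 1.15/0.9 = 69 and 81 × 1.15/0.9 = 103.5, so the total of 210 stands. Recruitment, data collection and care are unaffected.

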5.0 PRIMARY OUTCOMES

- 5.1 Foley's catheter insertion to delivery interval
- 5.2 Maternal satisfaction with the labour induction process

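### Section 6.1 lets the trial's own data choose between a mean comparison and a rank test for the primary interval, with no criterion for the choice

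*Protocol*

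**What the plan says.** Section 5.0 of the Protocol lists "Foley's catheter insertion to delivery interval" as the first of two primary outcomes. Section 6.1 names no test for it. It gives one general rule for all outcomes: "Normally distributed continuous data will be analysed with paired Student's t test", chi-square for categorical data, and for the rest the Mann-"Whitney U test will be used on non-normally distributed or ordinal data". Because the interval is continuous, its test is settled only once its distribution has been judged. Section 6.1 does not say how or when that judgement is made, or which effect estimate goes with each test.

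Section 4.5 shows that the switch is intended. It sizes the interval with a t test ("applying alpha of 0.02 (Bonferroni correction for 2 primary outcomes), t test, 80% power, 1 to 1 ratio") on "18.0 hours with SD 6.8 vs 22.6 hours SD 8.2". It then adds 15% with the reason "Factoring in the possibility of non-normal data distribution requiring Mann Whitney U test application". Section 4.4 states that blinding is not possible.

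The other primary outcome, the 0-10 satisfaction score, is not affected. Section 4.5 treats it as ordinal, so section 6.1 sends it to Mann-Whitney in any case.

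**The concern.** The two branches answer different questions. The t test concerns the difference in mean hours. Mann-Whitney concerns whether intervals in one arm tend to rank below those in the other; it neither tests nor estimates a mean difference. The primary hypothesis for the interval therefore depends on how the outcome data look.

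Normality has no single definition. A histogram, a skewness statistic, a Shapiro-Wilk test, a Kolmogorov-Smirnov test, pooled data or each arm separately can all give different answers. With no criterion written down, the analyst of an unblinded trial can see both p values before settling which test the data called for. A reader could not later verify that the reported test was not simply the more favourable one.

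**Working it through.** **Inputs.** From section 4.5: means 18.0 and 22.6 hours, SDs 6.8 and 8.2, alpha 0.02 per primary outcome, 80% power, 1:1 allocation, 15% for Mann-Whitney, 10% dropout, final N = 210. Sidedness is not stated; two-sided reproduces the plan's figure.

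**Step 1: reproduce the plan's figure.**
- n per arm = (z for 0.99 + z for 0.80)² × (SD1² + SD2²) / difference²
- = 3.168² × (6.8² + 8.2²) / 4.6² = 10.036 × 113.48 / 21.16 = 53.8, so 54 per arm, as stated.
- 54 × 1.15 / 0.9 = 69 per arm, N = 138, as stated. (The total printed beside the 54 is 104; 2 × 54 = 108. This does not affect the 69.)
- Satisfaction gives 81 per arm, and 81 × 1.15 / 0.9 = 103.5. This outcome sets N = 210.

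**Step 2: power for the interval at the size actually planned.** 210 / 2 = 105 per arm; less 10% dropout, about 94. Power for 4.6 hours with a t test at two-sided 0.02 is 80% with 54 per arm, 90% with 69, 97% with 94 and 98% with 105.

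**Step 3: how often the rule would select Mann-Whitney.** The protocol gives neither the interval's shape nor a normality test, so both are assumed here. The rule simulated is Shapiro-Wilk p < 0.05 in either arm, then Mann-Whitney; otherwise an independent-samples t test. There were 4,000 trials per case with 94 per arm. Power uses the plan's means and SDs. Type I error uses one common distribution in both arms (mean 20.3, SD 7.5).

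| Assumed shape | Mann-Whitney selected | Power, t test | Power, Mann-Whitney | Power, two-stage rule | Type I error, two-stage rule |
|---|---|---|---|---|---|
| Normal | 10% | 96.7% | 96.0% | 96.7% | 2.0% |
| Gamma | 92% | 97.2% | 96.2% | 96.3% | 2.4% |
| Lognormal | over 99% | 96.7% | 97.8% | 97.8% | 1.6% |
| Gamma with a 6-hour floor | over 99% | 96.9% | 97.2% | 97.2% | 1.8% |

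With 54 to 105 per arm, the type I error of the two-stage rule ranged from 1.6% to 2.6% against 2%. Even reporting whichever test is significant gave only 2.3-2.8%.

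**Step 4: how often the choice changes the conclusion.** With 94 per arm at alpha 0.02, Welch's t test and Mann-Whitney disagree on significance in about 2% of trials at the planned 4.6 hours. At an assumed reduction of 2.5 hours (SD 7.5 in both arms) they disagree in about 8% if normal, 9% if gamma and 13% if lognormal.

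**Step 5: a tail of very long inductions.** Take the gamma case and assume that a fraction of women in both arms deliver 24 hours later. With 5%, power is about 86% for Welch and 92% for Mann-Whitney. With 10%, it is about 76% and 86%. These fractions are assumptions.

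**The case against.** The strongest objection is that nothing measurable is lost. The two-stage rule keeps type I error near 2% and power at 96-98%, section 6.1 ties the test to the distribution and not to the result, and a normality criterion is the kind of detail a statistical analysis plan often supplies. The figures stand. But the protocol has not left the matter open: it states a data-dependent rule for a primary outcome, and adding a criterion would still leave two possible hypotheses.

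Four stronger readings are tempting, and the documents do not support them.

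- *The trial will almost surely end up on Mann-Whitney.* The documents give no shape for the interval. The chance runs from about 10% to over 99%, depending on an assumed shape and an assumed normality test.
- *A rank test would betray the trial's question.* Sections 2.0 and 3.0 speak of a shorter interval, not of a mean. The phrase "a mean reduction of 4.6 hours in favour of 6-hour placement" belongs to section 4.5, where it describes the source used for sizing.
- *The trial is sized on the mean reduction.* That holds only for the interval's own calculation of 54, then 69 per arm. N = 210 comes from satisfaction, and the interval calculation already includes 15% for Mann-Whitney.
- *A rank test could gain nothing.* Section 4.4 allows further ripening after a failed first attempt, so a long upper tail is possible, and step 5 shows Mann-Whitney is then the more powerful test.

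**Conclusion.** The point holds as a badly fixed rule for a primary outcome. Section 6.1 lets the interval's own distribution decide which quantity is tested, with no criterion, in a trial that cannot be blinded.

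The harm is to what is tested and reported, and to whether a reader can trust the choice. It is not to power. Nor is it, to any material degree, to type I error, with the caveat that the error rates were simulated with both arms sharing one distribution. The two tests would reach different conclusions in about 2% of trials at the planned effect and about 8-13% at an assumed 2.5 hours. All simulated figures rest on the assumed shapes; the switching rates also rest on the Shapiro-Wilk rule.

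That one test should be fixed in advance is firm. Which one is a matter of judgement. This should be changed, and it is cheap to change.

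**What to change.** In section 6.1, name one independent-samples comparison for the insertion-to-delivery interval, to be used whatever the distribution, with its matching effect estimate and confidence interval. Name the other test as a sensitivity analysis. Either choice cures the defect:

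- **Welch's t test with the difference in mean hours.** This matches the t-test basis of section 4.5. Its cost is lost power if there is a tail of very long inductions: about 86% against 92% for Mann-Whitney with 5% of women delivering 24 hours later.
- **Mann-Whitney with the Hodges-Lehmann shift.** This matches the 15% allowance in section 4.5. Its cost is that it does not estimate the mean difference in which the interval calculation is expressed.

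In the same edit, replace the word paired with independent-samples, because the two arms are separate groups of women. It would also help to state outright that the satisfaction score is analysed with Mann-Whitney, as section 4.5 already assumes.

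The change is a few sentences. With 94 per arm, either test has at least 96% power for 4.6 hours under the four shapes in the table, so the sample size need not change.

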1.0 INTRODUCTION

In developed countries, approximately 20–25% of pregnant women will require labour induction (IOL) for various indications. (1) In considering IOL the benefits of an earlier delivery should outweigh the risks of continuing the pregnancy.(2) An unripe cervix is a risk factor for failed IOL and Caesarean delivery whereas prior vaginal delivery has the opposite impact. (3)

The two major techniques for cervical ripening are mechanical intervention and the use of pharmacologic agents.(4) Mechanical dilatation of the cervix may be via the transcervical placement of the single balloon catheter (i.e., Foley catheter). the double balloon catheter (i.e. Cook or Atard catheter) or with the use of osmotic dilator such as natural compound Laminaria, or synthetic compounds such as Lamicel and Dilapan.(5) Pharmacological forms of induction include prostaglandins and oxytocin.(6, 7) World Health Organization (WHO) strongly recommends the use of balloon catheter for induction of labor(8).

A lengthy induction process can increase adverse outcomes(1, 4, 9) and the burden on health care resources(10). Hence, it is clinically important to find an induction protocol that is efficient in order to reduce interval to delivery which in turn may increase maternal satisfaction.

Mechanical induction particularly with the single-balloon Foley catheter is widely used as the primary IOL method when cervical ripening is needed due to its low cost and reduced likelihood of uterine hyperstimulation compared to prostaglandins.(11) Studies have compared balloon catheter placement for 12 vs 24 hours finding that 12-hour placement results in shorter interval to delivery. (12, 13)

A recent study comparing 6 vs 12 hours placement with the double-balloon catheter has also shown reduction in the interval to delivery with the shorter placement period without increment in caesarean section rate. (14) Similarly, another study conducted using the double balloon catheter also but with only a single balloon inflated also shows shorter interval to delivery time in the 6-hour arm compared to the 12-hour group.(15) Both above-mentioned study used the costly double-balloon catheter. A 2017 meta-analysis (five randomized trials: 996 women) published in 2017, comparing single with double-balloon catheters for IOL shows the time from catheter insertion to delivery did not differ between the two types of catheters.(16)

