4.3 POPULATION OF STUDY

Multiparous women planned for elective induction of labour for various indications admitted will be assessed for enrolment using the Eligibility Form.

Eligibility form

Inclusion Criteria

•	Multiparous women (at least 1 vaginal delivery ≥ 24 weeks)	
•	Age ≥ 18 years	
•	Gestational age of ≥ 37 weeks	
•	Singleton pregnancy	
•	Cephalic presentation	
•	Intact membrane	
•	Reassuring fetal heart tracing	
•	Absence of significant contraction ≥ 2 in 10 minutes	
•	Successful Foley insertion for IOL	
•	Bishop score ≤ 5	

Exclusion Criteria

•	History of caesarean delivery or hysterotomy/ uterine	
	perforation/ previous myomectomy	
•	Latex Allergy	
•	Estimated Fetal weight less than 2kg or > 4kg	
•	Known major fetal malformations	
•	Contraindication for vaginal delivery	
•	Patient who is suspected COVID 19 infection or COVID 19 positive	

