6.0 SECONDARY OUTCOMES

based on core outcome set for trials on induction of labour: CROWN

Maternal outcomes

Change in bishop score after intervention

Use of additional method for cervical ripening

Time to delivery after Foley's catheter removal

Mode of delivery

- a) spontaneous vaginal
- b) vacuum
- c) forceps
- d) caesarean section

Indication for caesarean section

Duration of oxytocin infusion

Maternal satisfaction-based allocation to intervention until birth (11-point VNRS)

Blood loss during delivery

Third -or fourth-degree tear

Maternal infection

Use of regional analgesia in labour?

Length of hospital stay

ICU admission

Cardiorespiratory arrest

[figure not shown]
Hysterectomy

Apgar score at 1	L and 5 minutes				
NICU admission	ı				
Cord pH					
Neonatal sepsis					
Birth weight					
Birth trauma					
Hypoxic ischaer	nic encephalopath	ny/need for ther	apeutic hypothe	ermia	

Trial Protocol

Patient admitted to antenatal ward or labor ward.

PROTOCOL FLOW CHART

CASE REPORT F	CASE REPORT FORM				
	ment: / / _ (dd/ mm/ yy)				TUDY NUMBER
EDD://	(dd/ mm/ yy)				
Patient charact				PATIE	NT STICKER
Gravida:	Para: Abo	ortion:			
Gestational age	e:				
Latest recorded	d Weight:	kg			
Height:	cm				
Education level	l:				
Up to prim	ary				
Secondary					
Diploma					
Degree					
Masters					
PhD					
Occupation:					
Employed					
Self emplo	yed				
Student					
Housewife					
Other:					
Ethnicity:					
Malay					
Chinese					
Indian					
Other:					
Indication/s for	· IOL:	 			
Pre induction B	ishop Score:				
Score	0	1	2	3	
Dilatation	Closed	1-2 cm	3-4	5 cm	
Length	> 4 cm	3-4 cm	1-2 cm	0	
Consistency	Firm	medium	soft	-	

mid

-2

anterior

-1 to 0

+1, +2

≤ -3

Posterior

Position

Station

Primary Outcomes:

1. IOL to delivery interval [Date/Time delivery - Date/Time catheter inserted

[figure not shown]
2. Maternal satisfaction

Rate your satisfaction with the experience of your allocated intervention of placement (of 6 or 12 hours) of the Foley catheter for labour induction.

Circle your score below (higher score, greater satisfaction)

0	1	2	3	4	5	6	7	8	9	10

10-totally satisfied

To be assessed as soon as possible after delivery (in all cases before hospital discharge)

Dates and times

1.	Date / Time catheter inserted: / / (dd/ mm/ yy):: (hr:min)
2.	Date / Time catheter removed/ dislodged: / / (dd/ mm/ yy):: (hr:min)
3.	Date / Time ARM/SROM: / / (dd/ mm/ yy):: (hr:min)

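### Section 6.1 names only unadjusted tests and lets the interval test switch to a rank test, so the result may carry no difference in hours and two recorded baseline variables go unused

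*Protocol*

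**What the plan says.** Section 6.1 assigns a test to each type of data. For normal continuous data: "Normally distributed continuous data will be analysed with paired Student's t test". For the rest, chi-square is named for categorical data, and the Mann-Whitney "U test will be used on non-normally distributed or ordinal data". No covariate and no effect estimate is named.

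Section 4.5 sizes the interval outcome on means of 18.0 and 22.6 hours, a difference of 4.6 hours. It then adds 15% to the sample in case the interval is not normal and Mann-Whitney has to be used.

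Two baseline variables are available before allocation. In section 4.4, "Bishop score will be ascertained during the vaginal examination prior to Foley insertion", and allocation is revealed only after the catheter is successfully in place. Parity is among the patient characteristics on the case report form. Randomisation is in blocks of 4 or 8, with no stratification described.

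Section 6.0 lists "Change in bishop score after intervention" as a secondary outcome. The introduction says: "An unripe cervix is a risk factor for failed IOL and Caesarean delivery whereas prior vaginal delivery has the opposite impact". Eligibility in section 4.3 requires "Bishop score ≤ 5" and at least one earlier vaginal delivery.

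**The concern.** The objective and hypothesis (sections 2.0 and 3.0) ask whether earlier removal shortens the time to delivery, and the planning figure is a mean difference in hours. If the interval looks skewed, section 6.1 moves to a rank comparison. That test alone answers whether one arm tends to deliver sooner, not by how many hours. A shift estimate in hours could be attached to it, but none is named, and it would not be the mean difference used for planning. What the trial estimates for a primary outcome would therefore depend on how the data look.

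The second issue is precision. A variable measured before allocation can be put in the model without bias, and it narrows the confidence interval to the extent that it predicts the outcome. Pre-induction Bishop score and parity are natural candidates and are already collected. For Bishop change, the baseline is part of the outcome itself. Testing raw change fixes the baseline coefficient at 1, whereas ANCOVA estimates it and in large samples is never less precise.

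**Working it through.** **1. The plan's own sample size.** Inputs from section 4.5: two-sided alpha 0.02, power 80%, 1:1 allocation. With z = 2.326 and 0.842, n per arm = (2.326 + 0.842)² × (SD₁² + SD₂²) / difference².

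- Interval: 10.04 × (6.8² + 8.2²) / 4.6² = 10.04 × 113.48 / 21.16 = 53.8, so 54. Inflated: 54 × 1.15 / 0.9 = 69.
- Satisfaction: 10.04 × (2² + 2²) / 1² = 80.3, so 81. Inflated: 81 × 1.15 / 0.9 = 103.5.

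Both match. The total of 210 rests on unadjusted two-sample comparisons and is set by satisfaction.

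**2. Power already in hand.** Of 105 women per arm, 10% dropout leaves 94.5. Dividing by the 15% rank-test allowance leaves an effective 82.2. Unadjusted power is then 94.4% for the interval and 81.0% for satisfaction.

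**3. What adjustment could add.** The protocol gives no R-squared for Bishop score and parity with either primary outcome, so a range from 0 to 0.20 is assumed, the same in both arms. The unadjusted standard error of the interval difference at 94.5 per arm is √(113.48 / 94.5) = 1.10 h. Adjustment multiplies it by √(1 − R²). The 98% half-width is 2.326 × SE. Power is at the effective 82.2 per arm.

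| Assumed R² | SE (h) | 98% half-width (h) | CI narrower by | Interval power | Satisfaction power |
|---|---|---|---|---|---|
| 0 | 1.10 | 2.55 | 0% | 94.4% | 81.0% |
| 0.02 | 1.08 | 2.52 | 1.0% | 94.8% | 81.9% |
| 0.05 | 1.07 | 2.48 | 2.5% | 95.5% | 83.2% |
| 0.10 | 1.04 | 2.42 | 5.1% | 96.4% | 85.4% |
| 0.20 | 0.98 | 2.28 | 10.6% | 98.0% | 89.6% |

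**4. Bishop score: ANCOVA against raw change.** Let r be the correlation between first and second score and k the ratio of second to first SD. Both are assumed, as the protocol gives neither. The variance of the ANCOVA estimate relative to the raw-change estimate is k²(1 − r²) / (k² + 1 − 2rk).

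| k | r = 0.2 | r = 0.3 | r = 0.5 |
|---|---|---|---|
| 1 | 0.60 | 0.65 | 0.75 |
| 1.5 | 0.82 | 0.87 | 0.96 |
| 2 | 0.91 | 0.96 | 1.00 |

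The first score is capped at 5 by eligibility and the second is not, so k above 1 is plausible. The saving therefore runs from about 40% of the variance down to almost none.

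**5. The confidence level.** Section 4.5 uses alpha 0.02 for each primary outcome, which pairs with a 98% interval. An even Bonferroni split of 0.05 over two outcomes is 0.025, which pairs with 97.5%. The interval reported has to follow whichever alpha is kept.

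**The case against.** The strongest reply is that nothing here is wrong. Unadjusted two-sample tests are valid under randomisation, the trial was sized on them, and a 15% allowance was made for the rank test. Chance imbalance under unstratified randomisation is already covered by the standard error and the type I error; it is not bias. Covariate adjustment is often left to a statistical analysis plan, one may exist, and section 6.1 does not forbid adjustment. All of that stands, except that it does not put the point out of scope: the protocol itself names the tests, and as named they take no covariate and let the distribution choose between a mean and a rank comparison.

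A reader might infer that the protocol itself identifies both covariates as strong predictors of the interval. It does not. The introduction ties an unripe cervix and earlier vaginal delivery to failed induction and caesarean delivery, not to time to delivery or satisfaction. Eligibility then makes both factors, as worded there, the same for every woman. What remains is variation in Bishop score from 0 to 5 and in the number of earlier births, and the protocol says nothing about how well either predicts the interval.

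A reader might also infer a large, certain gain at no cost. The R-squared is unknown and could be near zero, interval power is already about 94%, and a large saving on Bishop change needs nearly equal spread before and after ripening. Nor is the change entirely free, because Mann-Whitney takes no covariate and the primary estimate would change in kind.

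**Conclusion.** The point holds as an improvement in efficiency and in what is reported, not as an error that threatens the trial. The firmer part needs no assumption about prediction: under section 6.1 a skewed interval leads to a rank test that does not give the hours saved, although the trial was designed around 4.6 hours. A model fixed in advance always gives that figure.

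The precision part is real in direction but uncertain in size. Over an assumed R-squared of 0 to 0.20, the confidence interval for the interval difference narrows by 0 to about 11% (standard error 1.10 h down to 0.98 h). For the second Bishop score, ANCOVA saves between almost nothing and about 40% of the variance over the assumed correlations and SD ratios. The documents do not support a claim that the planned tests are invalid or that the trial is underpowered for the interval.

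The word paired for the t test in section 6.1 does not fit two independent arms. It is a separate error and adds no weight here, but the supportive test below should be named correctly.

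**What to change.** Before any outcome data are seen, amend section 6.1 as follows.

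- Make the primary interval analysis a linear regression of insertion-to-delivery time on arm, pre-induction Bishop score and parity, with robust standard errors, whatever the distribution. State how parity enters the model.
- Report the adjusted difference in hours with a 98% confidence interval if alpha stays at 0.02, or 97.5% if it is restated as 0.025.
- Keep the unadjusted independent-samples t test or Mann-Whitney test as a supportive result.
- Analyse the second Bishop score by ANCOVA, with arm and the first score in the model, in place of a test on raw change.
- If a statistical analysis plan exists and already sets this out, align section 6.1 with it.

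The cost is a few sentences and a little more analysis. No new data and no change to the sample size are needed, as both covariates are on the case report form. The small downside is that, with skewed data, the primary estimate becomes an adjusted mean difference and no longer a rank comparison. The supportive test keeps the rank result visible.
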